### **Progression from Islet Autoimmunity (IA) to T1D**

Hypothesis 1.1: Persistent IA triggered after age 6 y results in T1D diagnosis in early adulthood

Hypothesis 1.2: Transient childhood IA does not increase the risk of diabetes in early adulthood

As of 10/2015, 94 children participating in DAISY follow-up have developed T1D. All but one had expressed IA prior to or at diagnosis. Over 70% of children expressing two or more autoantibodies progressed to T1D in 10 years since seroconversion, compared to 15% of those with one autoantibody. There was little difference in progression by family history of T1D or presence of the HLA-DR3/4,DQB1\*0302 genotype. PTPN22 and UBASH3A and INS predicted diabetes, controlling for family history of T1D and presence of HLA-DR3/4-DQB1\*0302 genotype. In general population children, risk alleles at these 5 genetic markers conferred combined HR of 13 for IA and >40 for T1D. INS, UBASH3A, and IFIH1 were significantly associated with progression from IA to T1D, while PTPN22 and IL27 showed a borderline association. Age of appearance of first autoantibody and mean IAA levels during the follow-up were major determinants of the age at diagnosis. In contrast, levels of GAA or IA-2A did not predict time to progression to diabetes.

***New assays for insulin/proinsulin and GAD autoantibody detection:*** Serial serum samples from DAISY participants followed from birth who progressed to T1D were essential in development of novel assays for insulin/proinsulin autoantibodies (IAA), GADA and TGA. These nonradioactive electrochemiluminescence-based assays have been developed on a platform from MesoScale Discovery (MSD). The ECL-IAA assay detects onset of IA earlier than any current standard radioassays in 24% of children, thus defining more precisely the onset of IA and timing of potential triggering events. Both ECL-IAA and ECL-GADA assays are more specific for high-affinity autoantibodies that predict progression to T1D. Next, the individual ECL assays were adapted to measure four antibodies in a single well using a small blood volume (6ul). Using a MSD QuickPlex 4-Spot plate or U-Plex plate, we successfully combined ECL-IAA, GADA and IA-2A with transglutaminase autoantibodies (ECL-TGA) in a single well of a 96 well plate. The multiplex ECL

[figure not shown]
assay was more sensitive than current radioassays for IAA and TGA and will facilitate high-throughput screening for T1D and celiac disease risk.

**Risk of T1D in subjects with a single islet autoantibody**

Nearly a half of children with IA persistently express a single autoantibody: 46% in DAISY, 45% in combined DAISY, BABYDIAB and DIPP cohorts and 40% in TEDDY. Fewer than 15% of these children progress to diabetes in 10 years.

Those who do progress, typically have high-affinity islet autoantibodies. The ECL-based IAA and GADA assays detect only high-affinity autoantibodies and efficiently classify single islet autoantibodies into high-risk vs. no risk (**Figure 5**).

**Figure 5: High rate of progression to T1D among subjects with a single persistent islet autoantibody by radioassay, confirmed as high-affinity by ECL; 29% and 35% risk of T1D in 5 and 10 years**

**Laboratory** Serum samples are stored at -70°C prior to testing. All measurements are performed on coded samples with blinded duplicate testing of all positive and 5% of negative samples. Islet autoantibodies are measured, in the laboratory of [name] (the reference laboratory for TrialNet, TEDDY and T1DGC). In the Diabetes Autoantibody Standardization Program (DASP) workshop, sensitivity and specificity were, respectively, 72% and 99% for GAA, 62% and 99% for IA-2A, 62% and 99% for ZnT8A, and 48% and 100% for IAA. Transplacental autoantibodies are excluded. TG IgA autoantibodies are measured at all visits (by R01 DK-50979). TPO (with TSH and T4, if positive), autoantibodies to 21OH (adrenal) and to cyclic citrullinated peptide (rheumatoid arthritis) - will be re-measured only once at age 20 or the end of the follow-up. Standard methods will be used to measure: HbA1c, blood glucose, fasting total-, HDL-cholesterol and triglycerides. Adiponectin, insulin and C-peptide will be measured using radioimmunoassays.

**Assessment of dysglycemia** Participants with persistent IA are asked to complete an oral glucose tolerance test (OGTT) annually. Earlier diagnosis and treatment of T1D may be also possible by applying continuous glucose monitoring (CGM). In a case-control study nested in DAISY, we documented that CGM can detect early hyperglycemia in children with persistent IA and no symptoms of diabetes. More than 20% of CGM time spent above 140 mg/dL predicted progression to diabetes. The IA cases had mean HbA1c of 5.5% (37 mmol/mol), however, their average maximum daytime glucose value was higher, and they had increased glycemic variability on CGM. We will record CGM for 1-2 weeks after each clinic visit in all participants with IA to monitor evolution of dysglycemia during progression to T1D (letter of collaboration from [name], Dexcom).

Hypothesis 1.3: Sedentary life-style and insulin resistance predict faster progression from persistent IA to T1D

**SIGNIFICANCE:** The environmental factors influencing the risk and rate of progression from IA to T1D remain poorly understood; accelerated growth or insulin resistance, due to obesity, puberty or physical inactivity, could contribute to risk. Habitual physical activity is associated with lower HbA1c, higher c-peptide, and lower insulin requirements at diagnosis of T1D and up to 2 y later. To fully ascertain predictors of progression to T1D (related also to non-autoimmune forms of adult diabetes), anthropometry, dietary factors (glycemic index, intake of fat and added sugars), pubertal stage, and physical activity must be measured prospectively and repeatedly. We hypothesize that IR, increased by puberty, central obesity, poor diet and physical inactivity, will predict progression from IA to T1D.

**INNOVATION:** Most prior studies of growth, obesity, insulin resistance and progression to T1D have examined children prior to or at puberty. However, less is known about the relationship

between the evolution of these factors that tends to occur among youth and young adults and progression to diabetes. As DAISY study participants reach that age, this is an ideal time to examine how changes in adiposity, physical activity and insulin sensitivity may contribute to the risk of T1D.

**APPROACH: Preliminary studies** DAISY added measurement of waist circumference and physical activity questionnaire at each visit starting in June 2010; these measurements are available on 1,090 subjects. Pubertal stage has been determined based on self-reported Tanner Stage at each visit. In 2011, we began collecting objective physical activity data using an accelerometer - a small device worn on the hip or lower back to measure change in velocity over time - worn for 7 days. We have identified 126 antibody positive subjects as eligible for this more intensive measurement of physical activity. We have obtained accelerometer data for 82 subjects, 69 of which have worn the accelerometer more than once; 8 have later developed T1D. We have also obtained accelerometer data one time on 55 antibody negative controls. Multivariate linear regression analysis, adjusted for age, sex, BMI, and total time recorded has shown that IA subjects spent a higher percentage of time sedentary than controls (p=0.045), less time engaged in vigorous physical activity (p=0.01), and took fewer total steps (p=0.02) and steps per minute (p=0.03). In a cross-sectional analysis, these differences translated into IA subjects spending over 110 extra minutes sedentary and 70 fewer minutes engaged in vigorous physical activity per week, compared to controls. In March of 2020 DAISY stopped offering accelerometers to participants that are antibody positive or are antibody negative controls.

**Prospective dietary data** We will continue to measure dietary intake of macronutrients, glycemic index and added sugars using a validated Youth/Adolescent Questionnaire completed by both parents and child between ages 10-12 and by the participant after age 12 on the entire DAISY cohort. In the IA positive subjects and the controls,

**Anthropometry** Weight will be measured using a calibrated digital scale to the nearest 0.1 kg, height using a wall-mounted stadiometer to the nearest 0.1 cm. Minimal waist circumference will be measured using a Figure Finder tape (Novel Products, Rockton, IL). Body fat percentage will be measured using bioelectrical impedance analysis (TANITA Dc-430 U Dual frequency Total Body Composition Analyzer), which is a fast, inexpensive and low-risk alternative to DXA. Fat distribution may be important in the development of type 1 diabetes (T1D). By measuring body fat in DAISY, we can better analyze factors related to being overweight or obese.

## **Specific Aim 2. Validate candidate proteomic biomarkers of IA and T1D, in a nested-case study of 213 youth with persistent IA and 213 controls.**

**SIGNIFICANCE:** Progress in proteomic technology has made it applicable to epidemiologic studies. Prospective evaluation of the proteome contemporary with development of IA, or progression to T1D can help to discover underlying pathways and potential therapeutic targets. Cross-sectional studies of serum proteome at diagnosis of T1D have suggested, not surprisingly, involvement of inflammation and innate immunity. However, samples used in these studies were collected shortly after T1D diagnosis, reflecting late stages of  $\beta$ -cell destruction and hyperglycemia. In contrast, prospective cohorts allow profiling of the proteome as children develop IA and progress to T1D and in aged-matched controls. Several published and unpublished discovery studies have generated multiple protein candidates, but little consistency. This highlights the need for replication in larger studies, able to control for heterogeneity of pre-T1D phenotypes and confounders, e.g., age and sex, but also for genetic background and environmental exposures. DAISY has collected a unique dataset and serum/plasma samples for the high-power targeted protein analysis proposed below. The goal of this study is to help form consensus regarding proteomic biomarkers of IA and T1D and underlying pathways. The analytical platform proposed here is capable of quantification of low-abundant proteins, likely to be found in the earlier stages of disease, that can be masked by more abundant proteins.

[figure not shown]
**INNOVATION:** So far, none of the 'omics biomarkers reported to predict progression from IA to T1D have been confirmed by independent studies. Using targeted proteomics we will validate candidate peptides/proteins reported from several discovery studies. The analyses will cover an

unprecedented age-span of diabetes diagnosis (0-25 y) while controlling for an apparent heterogeneity of IA phenotypes, age, sex and ethnicity.

**APPROACH:** We will characterize differences in the abundances/profiles of ~75 target proteins in a nested case-control study of 213 youth persistently positive for IA and 213 controls, frequency matched on age, sex and ethnicity (79% NHW). As of 9/2015, 89 cases have developed T1D (at mean age  $9.6 \pm 4.6$  y), 61 were persistently positive for  $\geq 2$  islet autoantibodies or one high-affinity autoantibody and 63 were positive for one low-affinity autoantibody (**Figure 6**). These three subgroups of youth represent heterogeneity of the IA phenotypes that show, respectively, rapid, slow and no progression to T1D (see Figures 4 and 6, above).

**Hypothesis 2.1:** A reproducible set of proteomic biomarkers will predict development of IA independently of demographic factors and HLA class II genotypes.

**Hypothesis 2.2:** A reproducible set of proteomic biomarkers will predict the rate of progression from IA to T1D independently of demographic factors, HLA class II genotypes.

**Figure 6:** Proposed nested case-control study of targeted proteomics.

Serial samples collected at 4-time points per subject will be analyzed.

**Preliminary data:** Two nested cases-controls DAISY proteomics discovery studies have identified proteins associated with development of IA and/or progression to T1D (**Table 3**). In **DAISY1**, one of the 4 proteins identified by the aptamer-based approach as strongly associated with IA and T1D (CNDP1,  $p=1.22e^{-07}$ , q-value 0.00013) was independently confirmed in a different laboratory using the LC-MRM/MS approach.

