newborn screening programs. This study is likely to exert a sustained, powerful influence on diabetes research by using prospectively defined immuno-genetic phenotypes to advance both personalized medicine and public health approaches to screening and early interventions.

**APPROACH:** We will follow the already established cohort of youth at high risk of T1D and other autoimmune diseases (current n=1149, median age 17.2 y, IQR 13.5-20.2 y) to estimate the overall burden of pre-clinical and clinical T1D, celiac, thyroid, adrenal, rheumatic and parietal autoimmune disease in Colorado by age 25. This will inform future screening and prevention programs. We will further explore the apparent heterogeneity of IA and its implications for adult-onset diabetes.

**Study Population:** Since 1994, DAISY has studied two large cohorts of high-risk children: A) 1,424 general population newborns with high-risk HLA-DR,DQ genotypes; and B) 1,123 non-diabetic relatives of patients with T1D. Cohort to date: 222 persistent IA and 94 progressed to T1D, 5 died, 3 disenrolled due to medical conditions, 265 lost to follow-up; 2180 participants are being tracked and 1149 complete study visits.

General Population High-risk Children During 1993-2004, 31,881 newborns from the general population of Denver, Colorado were screened for HLA-DR,DQ genotypes carrying susceptibility to T1D. 90% of all children born at the St. Joseph's Hospital have participated, representing closely the ethnic breakdown of the Denver Metropolitan Area and including children classified by their mothers as non-Hispanic white (56%), Hispanic (30%), African American (7%), Asian American (2%) or biracial/other (5%). Throughout this application, "DR4" denotes DR4,DQB1\*0302. All children with DR3/4, DR3/3 and DR4/4 and a sample of those with DR4/x or DR3/x were invited to participate in follow-up at ages 9, 15, and 24 months and yearly thereafter; 1,424 completed at least one visit.

Non-diabetic Relatives Non-diabetic offspring and siblings of patients with T1D were invited to participate through the BDC clinics and regardless of their HLA genotype; 1,123 enrolled, at median age 1.4 y and are followed identically to the general population cohort.

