**Plasma proteomics of The Environmental Determinants of Diabetes in the Young (TEDDY) consortium.** [name] PNNL lab is currently analyzing the plasma proteome of 368 individuals enrolled in the TEDDY program, searching for signatures of pancreatic  $\beta$ -cell death, systemic responses to autoimmunity and development of type 1 diabetes. So far, samples from 180 individuals were analyzed by LC-MS/MS, which led to the identification of over 19,000 peptides derived from approximately 1,500 proteins. Data capture is still ongoing, and a statistical analysis has not yet been performed.

**Signatures of pancreatic  $\beta$ -cell stress - Beta Marker** - NIH-funded project of the Human Islet Research Network (HIRN) ([name] & [name], PIs). To study pancreatic  $\beta$ -cell stress and potential mechanisms of death, a proteomic analysis of pancreatic islets treated with the cytokines interferon- $\gamma$  and interleukin 1 $\beta$  is being performed. Preliminary data from the analysis of samples from 4 donors led to the identification of 4,810 proteins, of which 47 were differentially abundant after cytokine treatment.

**Target selection.** Targeted proteins will be selected based on three criteria: (i) **high priority** candidates that are consistently statistically significant in multiple cohorts (and DAISY, DIPP, TEDDY, BetaMarker, BABYDIAB and others), (ii) **moderate priority** candidates significantly different in only one study, but with a high fold change, and (iii) **low priority** candidates based on significant differences only in one or more studies. We anticipate that a subset of the peptide/protein markers (approximately 150 peptides corresponding to 75 proteins) will be assayed in targeted measurements.

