Statistical analyses will be carried out by [name] (PNNL) – see letter of collaboration. The relative quantification data will be normalized to the reference sample, log transforming (base 2), and then median centered. First mixed effects linear models, with a normal conditional distribution and identity link function, will be fit separately to cases and controls using R and the lme4 package. Age and sex will be used as the fixed effects in these models including linear and quadratic models to examine trends in abundance over time and random effects for each subject will be included to account for the subject variability and non-independent nature of the data over time. Likelihood ratio tests will be conducted with ( $\alpha = 0.05$ ). A difference in trends between cases and controls will be quantified by fitting the mixed effects linear/quadratic models and including a fixed effect to account for different mean intercepts, slopes and quadratic terms, where applicable, for each group. Additionally, a likelihood ratio test between a model including and not including case-control status as an effect can be used to determine differences in intercept, slope, and/or quadratic mean trends. The highest degree model that is statistically significant for at least one group will be fit with fixed effects for age and group and an interaction term between age and group (allowing for separate slopes for each group) and a random effect for subject.

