Detecting a significant difference in trends cases and controls is by testing if the group regression parameter is equal to 0, which is rejected when the true population parameter is different from 0. In the case of a linear trend, this involves the following t-test:  $t_{\alpha, n-4} = b/s_b$  where  $\alpha$  is the type 1 error rate,  $b$  is the estimated regression parameter,  $s_b$  is the standard error of the regression parameter estimate. The standard error of the regression parameter estimate depends on the overall variability of the data, the number of subjects (n) and the number of time points per subject (T). A power analysis was conducted based on a simulation study. From the previous DAISY1 study, the 75th percentile absolute value estimated slope due to group membership was  $b = 0.005$  and the overall error variances were calculated for each peptide. **Table 4** gives the power of the above test for select combinations of number of subjects and time points per subject for the 90th percentile of error variances. There will be a sufficient power to test the hypotheses with 4 or more samples per subject even in a subgroup analysis with 25 subjects per subgroup. For instance, a sample size of 20 subjects per group and 4 time points per subject will provide at least 82% power at the 90th percentile of the observed error variances.

Number of subjects/group	Number of time points/subject					
	3	4	5	6	7	8
30	.89	.99	1	1	1	1
25	.77	.90	.96	.99	1	1
20	.60	.71	.82	.89	.95	.98
15	.34	.43	.57	.52	.70	.84

The mixed model approach is typically preferred to ANCOVA with repeated measures for this type of data. ANCOVA's limitations include sensitivity to missing observations and restrictive variance-covariance structures. Additionally, mixed models naturally handle uneven spacing of

repeated measurements, tend to be more interpretable and will lead to natural tests for comparing groups.

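### Aim 2 is presented as validation, but its case set must contain most of the DAISY discovery cases, and its tests use α = 0.05 with no error control named across about 75 proteins

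*Protocol*

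**What the plan says.** The aim reads "Validate candidate proteomic biomarkers of IA and T1D, in a nested-case study of 213 youth with persistent IA and 213 controls". The Approach describes the set as "213 youth persistently positive for IA and 213 controls, frequency matched on age, sex and ethnicity" and adds "As of 9/2015, 89 cases have developed T1D". The Study Population paragraph under Aim 1 gives the pool from which these cases come: "222 persistent IA and 94 progressed to T1D".

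The preliminary data state "Two nested cases-controls DAISY proteomics discovery studies have identified proteins associated with development of IA and/or progression to T1D". Table 3 lists DAISY1 (25 T1D, 20 IA-positive without diabetes, 25 controls; 4 and 1 targets on two platforms) and DAISY2 (11 T1D, 15 IA-positive without diabetes, 10 controls; 142 targets). It also lists DIPP (15 targets) and further outside sources. The 142 DAISY2 proteins were those differing between T1D and control children at p < 0.05. Target selection admits candidates significant in a single study and expects "approximately 150 peptides corresponding to 75 proteins".

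In section F (Data Analysis Plan), the Aim 2 text says "Likelihood ratio tests will be conducted with" α = 0.05. For the case-control trend test it says only that α "is the type 1 error rate". It names no correction across proteins. Neither the Aim 2 research plan nor the Aim 2 part of section F says what happens to children who were in DAISY1 or DAISY2.

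**The concern.** The Innovation paragraph of Aim 2 says that no omics marker of progression from IA to T1D has yet been confirmed independently, and it offers this study as the remedy. Two features work against that.

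First, a candidate chosen because it differed in certain children is tested again in a set that contains many of those children. Part of the chance difference that nominated it carries over.

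Second, a panel of about 75 proteins tested at 5% each yields false positives even in wholly new children, unless nearly every candidate is real. The single-study entry route makes that hard to assume.

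At stake is what a positive Aim 2 result can be taken to mean. As written, it could not be reported as independent confirmation of the DAISY-nominated markers.

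**Working it through.** **Plan's own power figure.** The Aim 2 power comes from a simulation whose error variance and visit spacing are not given, so it cannot be rebuilt. The text gives at least 82% for 20 subjects per group and 4 time points. Table 4 shows .71 for that cell; .82 is the 5-time-point cell. I therefore calibrate below on the cell for 25 subjects and 4 time points (.90).

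**Forced overlap of cases** (the 213 are taken as drawn from the 222):
- Persistent-IA children outside the Aim 2 set: 222 − 213 = 9. T1D children outside: at most 94 − 89 = 5.
- DAISY1 cases inside: at least 45 − 9 = 36. DAISY1 T1D inside: at least 25 − 5 = 20.
- DAISY2 T1D inside: at least 11 − 5 = 6. If the DAISY2 IA-positive children had persistent IA, at least 26 − 9 = 17 of its 26 cases are inside.
- Controls: the counts force no overlap. It can be anything from none to all 25 and all 10.

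**Multiplicity** (m₀ null proteins, α = 0.05, independent tests): expected false positives = 0.05·m₀; chance of at least one = 1 − 0.95^m₀.

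| Null share of 75 | Expected false positives | Chance of at least one |
|---|---|---|
| all (75) | 3.75 | 98% |
| half (37.5) | 1.9 | 85% |
| a tenth (7.5) | 0.4 | 32% |

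For 150 peptides, all null, the expectation is 150 × 0.05 = 7.5.

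**Re-use, DAISY2 candidates.** Take a null protein selected at two-sided p < 0.05 in 11 T1D against 10 controls, then tested again in N cases against 213 controls. Let c of the 11 cases and k of the 10 controls be re-used with the same measurements. Under a simple mean-difference model the two z-statistics have correlation

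r = [c/(11N) + k/(10·213)] / √[(1/11 + 1/10)(1/N + 1/213)].

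The re-pass rate is the bivariate normal probability that both are significant, divided by 0.05.
- Full set, N = 213: c = 6, k = 0 gives r = 0.060 and 5.2%. c = 11, k = 10 gives r = (2/213)/√(0.1909 × 2/213) = 0.222 and 7.6%.
- T1D subset, N = 89: c = 6, k = 0 gives r = 0.111 and 5.7%. c = 11, k = 10 gives r = 0.289 and 9.4%.

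**Power after the change.** The .90 cell implies a noncentrality of 1.282 + 1.960 = 3.242 at 25 per group. Scaling by √(n/25), power at the strict level 0.05/75 = 0.00067 (critical value 3.403) is Φ(3.242·√(n/25) − 3.403):
- n = 142: 1.00
- n = 53: 0.91
- n = 25: 0.44

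Table 4 does not follow this scaling exactly. At 4 time points it predicts .94, .83 and .71 for 30, 20 and 15 per group, where the table has .99, .71 and .43.

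**The case against.** The best case for the plan runs as follows.

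- **The overlap is inferred, not stated.** True, but the case bounds follow from the protocol's own figures. The different dates (9/2015 for the 89, 10/2015 for the 94) do not loosen them: a child in the set diagnosed in between would leave fewer T1D children outside it. The DAISY2 figure of 17 does need its IA-positive children to have had persistent IA, which Table 3 does not say. The 6 of 11 T1D cases does not need it.
- **Re-use does little.** For DAISY2, which supplies most of the DAISY-nominated targets, this stands. A reader might infer re-pass rates of 12–20%. Those figures come from applying a p < 0.05 selection to DAISY1 and assuming that controls overlap in proportion. The protocol does not say that DAISY1 targets were picked at p < 0.05. It calls them strongly associated and gives p = 1.22e-07 and q = 0.00013 for CNDP1. Control overlap is not forced. Aim 2 also uses a different assay and may use different samples, which lowers the correlation further.
- **Outside candidates are untouched.** This stands for DIPP, TEDDY, BABYDIAB and BetaMarker: DAISY is a separate population for them. Multiplicity still applies to them.
- **α = 0.05 is attached to the within-group trend models, and a separate analysis plan could add a correction.** Both are fair. Yet section F is itself a data analysis plan. It fixes the models and the only α value given for Aim 2, and it leaves intercept, slope and quadratic differences as alternative routes to significance. The q-value and false discovery rates elsewhere in Aim 2 describe earlier studies.
- **Candidates seen in several cohorts have top priority, so many may be real.** This stands as a limit on the size, and it is why the null share is shown as a range.

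**Conclusion.** The point holds in a bounded form. On the protocol's own counts, at least 36 of 45 DAISY1 cases (at least 20 of 25 T1D) and at least 6 of 11 DAISY2 T1D cases are in the set called validation, with no exclusion or separate analysis stated. The Aim 2 analysis names α = 0.05 and no error control over about 75 proteins.

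Multiplicity is the main source of error, and its size depends on the unknown null share. Re-use adds a smaller upward bias, at most about 3 percentage points in the full set and 4 in the T1D subset for DAISY2 candidates, assuming the same measurements are used again.

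A reader might go further and infer that false markers are certain to be declared validated. The documents do not support that: 3.75 and 98% need every protein to be null, and the 98% also needs independent tests. What they do support is that a positive result for a DAISY-nominated protein, under the plan as written, would not be independent confirmation.

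**What to change.** 1. For each candidate nominated by DAISY1 or DAISY2, run the primary validation test without that study's participants, cases and controls alike. Report the full 213 + 213 as secondary. Candidates from outside cohorts keep the full set.
2. Use one test per protein: the likelihood ratio test of all group terms jointly, which section F already offers as a comparison of models with and without case-control status.
3. Control the Benjamini-Hochberg false discovery rate at 5% across the panel, and state that this defines a validated protein.

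No new samples or assays are needed. The cost is sample size for the DAISY-nominated candidates. If DAISY1 and DAISY2 are disjoint, lie wholly inside the set and are both removed, 45 + 26 = 71 cases leave and 213 − 71 = 142 remain, of whom 89 − (25 + 11) = 53 have T1D; 213 − 35 = 178 controls remain. Even at 0.05/75, which is stricter than the proposed false discovery rate, approximate power is 1.00 at 142 per group and 0.91 at 53.

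Small subgroups do lose power: about 0.44 at 25 per group. If all 20 + 15 = 35 non-diabetic discovery cases fell in the 61-child subgroup with multiple or high-affinity autoantibodies, 26 would remain, with power of about 0.46. Subgroup analyses near 25 per group should therefore be labelled exploratory. Because Table 4 departs from the scaling used here, the simulation should be rerun at the new level, and its 82% text figure reconciled with the .71 in the table.
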